2.2 Analysis sets

The analysis sets were defined in section 10 of the Clinical Study Protocol (CSP):

The Safety Set (SAF) consists of all patients treated with investigational drug (fingolimod) for whom safety information was collected. Of note, the statement that a patient has had no adverse events also constitutes a safety assessment.

The Full Analysis Set (FAS) consists of all patients treated with investigational drug (fingolimod) for whom data was collected and who have at least one post-baseline efficacy assessment. This is analogous to the ITT population.

The Per Protocol Population consists of all patients from the FAS population, for whom no major protocol violations are reported. All reported protocol violations will be classified as minor or major in a data review meeting prior to data base lock.

2.2.1 Subgroup of interest

No subgroup analyses are performed.

2.3 Patient disposition, demographics and other baseline characteristics

Background and demographic characteristics are presented using summary statistics for SAF, FAS and PPS.

2.3.1 Patient disposition

The disposition of all enrolled patients displays the number and reasons of screening failures.

The disposition of all patients in the treatment period (i.w. who received at least one dose of fingolimod) displays the number and reasons for premature discontinuation from the study.

2.4 Treatments (study treatment, rescue medication, concomitant therapies, compliance)

2.4.1 Study treatment / compliance

The total exposure (i.e., last fingolimod administration from study completion CRF – date of V2/D0/BL + 1 day) is displayed by sample statistics. It should be noted that patients are allowed to be pre-treated for 1 to 4 month according to the inclusion criteria. The total drug exposure per 100 subject years is presented also.

The interruption in fingolimod treatment is displayed by incidences, reason, number of interruption and total duration per patient.

2.4.2 Prior, concomitant and post therapies

Prior and concomitant medication is coded by WHO-DD. Frequencies of Anatomic Therapeutical Classes (ATC) and preferred terms within ATCs are displayed. Here, each patient with multiple medications is counted only once in that class.

2.5 Analysis of the primary objective

2.5.1 Primary endpoint

The primary endpoint is the change, i.e. difference, in mean RNFLT from baseline to month 36 (or last values in case of missing data) in the full analysis set. Mean RNFLT is the average of valid measurements of the right and left eye.

Sensitivity analyses are performed with the Per-Protocol Set (PPS) and for the relative change assessed by the M36/BL.

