The driving force of disability in MS is axonal loss. In MS, axonal loss seems to be associated with thinning of the retinal nerve fiber layer (RNFL). The RNFL contains ganglion cell axons that give rise to the optic nerve. Myelination of these fibers begins behind the eye, at the level of the lamina cribrosa (Frohman et al. 2008). The RNFL represents a unique region of the central nervous system because it lacks myelin and thus, allows for direct imaging of axons. It has therefore emerged as a highly interesting potential marker for the evaluation of axonal loss in MS. The thickness of the RNFL itself and the amount of change that may occur, however, are both very small (few microns) making a reliable assessment of RNFL thickness change challenging. Currently, optical coherence tomography (OCT) is the most accurate method to measure RNFL thickness.

Optical coherence tomography (OCT) is a validated, sensitive, non-invasive technique that uses low-coherence interferometry to obtain cross-sectional images of the retina. Commercially available OCT machines show good reproducibility of the measurement of RNFL thickness (Serbecic et al, 2010; Syc et al, 2010; Wu et al, 2010). With the latest technical improvements such as higher resolution and dual laser beam to overcome eye movements these instruments may have a high clinical utility in predicting MS disease course and determining treatment response.

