In MS, visible RNFL thinning by OCT may be seen when inflammation causes degeneration of axons within the optic nerve, e.g. as a result of optic neuritis (ON), a common manifestation in MS. However, RNFL thickness is reduced even in the absence of acute ON, making RNFL atrophy a potential structural biomarker of axonal injury or loss in the afferent visual pathway (Frohman et al, 2008; Barkhof et al, 2009; Talman et al, 2010). Cross-sectional studies in patients with MS have shown that RNFL thickness by OCT correlates with clinically relevant measures of disability like brain atrophy (Petzold et al, 2010) and cognitive decline (Toledo et al, 2008). Limited available longitudinal OCT data indicate that progressive RNFL thinning occurs over time in the eyes of MS patients and that this may correlate with change in clinically relevant parameters (Costello et al, 2009; Talman et al, 2010). A recent study in 299 MS patients with a mean follow-up of 18 months showed that progressive RNFL thinning observed over time (in eyes with and without prior history of ON) was associated with significant visual loss (Talman et al, 2010). Further studies are needed to evaluate if changes in RNFL are correlated also with global measures of disability in more detail (e.g. EDSS, patient reported outcomes, etc.).

To address this and to describe the change in RNFL thickness over time a global study is planned that includes RRMS patients (either untreated or treated with any approved MS disease modifying therapy) and a group of reference subjects (without neurologic or ophthalmic disease). Since the global study is not powered to particularly detect changes under fingolimod treatment – fingolimod is not even approved in all participating countries – the present study focuses on this subpopulation.

Fingolimod (FTY720; Gilenya[®]) is an oral, once daily disease modifying drug which has been approved for the treatment of relapsing MS in the US (on 21-Sep-2010), Europe (on 17-03-2011) and other countries.

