1.2 Study objectives and endpoints

The primary objective is to evaluate the change in average RNFL thickness (RNFLT) in RRMS patients treated with fingolimod over 36 months as assessed by OCT. The average RNFL thickness following OCT assessment will be calculated for the left and right eye per visit and per patient. The following table describe the objectives and endpoints:

	Objective	Endpoint
Primary	To evaluate the change in average RNFL thickness (RNFLT) in RRMS patients treated with fingolimod over 36 months as assessed by OCT	Absolute Difference in mean RNFLT from baseline (BL) to M36 (or last values in case of missing data) in the full analysis set (FAS). Mean RNFLT is the average of valid measurements of right and left eye. Sensitivity analyses are performed with the Per-Protocol Set (PPS) and for relative change (M36/BL)
Secondary	To compare changes in OCT parameters between eyes with and without history of optic neuritis	Absolute Difference in RNFLT from baseline (BL) to M36 (or last values in case of missing data) in the full analysis set (FAS) for: - eyes with versus without optic neuritis
Secondary	To evaluate the change in average RNFLT under fingolimod therapy from	Absolute Difference and ratios in average RNFLT from baseline (BL) to M12 respectively M24 (or last values in case of missing data) in the full analysis set (FAS).

	Objective	Endpoint
	baseline to months 12 and 24 as assessed by OCT	
Secondary	To evaluate change in quadrant RNFLT under fingolimod therapy from baseline to months 12, 24 and 36	
Absolute Difference and ratios in average quadrant RNFLT from baseline (BL) to M12, resp. M24 resp. M36 (or last values in case of missing data) in the full analysis set (FAS).
 
Quadrant RNFLT are:
 
 - Nasal-inferior - Nasal-superior - Temporal.inferior - Temporal-superior
Secondary	To evaluate changes in total macular volume (TMV) under fingolimod therapy from baseline to months 12, 24 and 36	Absolute Difference and ratios in average TMV from baseline (BL) to M12, resp. M24 resp. M36 (or last values in case of missing data) in the full analysis set (FAS).
Secondary	To evaluate changes in ganglion cell layer thickness (GCLT) under fingolimod therapy from baseline to months 12, 24 and 36	Absolute Difference and ratios in average GCLT from baseline (BL) to M12, resp. M24 resp. M36 (or last values in case of missing data) in the full analysis set (FAS).

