Secondary	To evaluate safety and tolerability of fingolimod in MS patients followed for up to 36 months and specifically to determine the frequency of macular edema under treatment with oral fingolimod in this patient population	
Incidence of adverse events, serious adverse events and (S)AEs at least possible related to fingolimod in the Safety Set (SAF)
 
Incidence of macular edema (AE of special interest)

Last value until Visit x The last (post-baseline) value documented until Visit x, i.e. missing or invalid data are replaced by the last available value. Baseline values are not carried forward.

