2.5.3 Handling of missing values/censoring/discontinuations

Missing values are replaced by the last available value. Post-baseline values are carried forward but no baseline values.

An analysis without replacing the missing data is performed as sensitivity analysis.

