2.7.3 Handling of missing values/censoring/discontinuations

Missing values are replaced by the last available value. According to the definition of FAS (at least one post-baseline value of the primary parameter is required) all patients have a value after baseline.

In contrast to the primary parameter no sensitivity analysis without replacing the missing data is performed.

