5.4 Rule of exclusion criteria of analysis sets

Table 1 *Protocol deviations that cause subjects to be excluded*

Deviation ID	Description of Deviation	Exclusion in Analyses
I1	Informed consent not obtained	Excluded from all analyses
I3	Subject aged < 18	Excluded from PP analysis
I4	Subject not diagnosed with RRMS	Excluded from all efficacy analyses
I5	Subject with EDDS > 6.0 at baseline visit	Exclude from PP analysis
I6	Subject not stable on Fingolimod for at least 28 days and at most 4 months prior to screening	Excluded from PP analysis
I7	Evidence of acute relapse within 30 days prior to baseline visit	Excluded from PP analysis
E1	Forbidden concomitant medication	Case by case review: excluded from PP analysis
E3	Subject is suffering from a cardiovascular condition	Case by case review: excluded from PP analysis (if relevant for primary parameter)
E4	Subject suffering from severe respiratory disease	Case by case review: excluded from PP analysis
E5	Subjects with history of specific MRI findings	Excluded from PP analysis
E7	Subject with a history of a malignancy of any organ system within the past 5 years	Excluded from PP analysis (Exception: localized basal cell carcinoma of the skin)
E8	Use of other investigational drug/therapy within 90 days or 5 half-lives of screening	Case by case review: excluded from PP analysis
E9	Pregnant or nursing women	Excluded from PP analysis
E10	Subject with any ophthalmologic reason for RNFL pathology other than MS	Case by case review: excluded from PP analysis
E11	History or active severe myopia	Case by case review: excluded from PP analysis
E12	Acute optic neuritis within the last 6 months prior to screening	Excluded from PP analysis

Deviation ID	Description of Deviation	Exclusion in Analyses
E13	Evidence of advanced diabetic retinopathy	Excluded from PP analysis
E14	Presence of retinal conditions	Case by case review: excluded from PP analysis
E15	Concomitant use of drugs that may directly affect retinal structure and function	Case by case review: excluded from PP analysis
S1	Treatment regime changed	Excluded from PP analysis
O1	Baseline OCT measurements not performed	Excluded from PP analysis
O3	Difference between visit 7 and baseline \leq 1035 days	Excluded from PP analysis

Table 2 Subject Classification

Analysis Set	PD ID that cause subjects to be excluded	Non-PD criteria that cause subjects to be excluded

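### The primary endpoint averages whichever eyes are valid at each visit, so losing or gaining one eye creates a false change of half the inter-eye difference

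*SAP*

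**What the plan says.** SAP 2.5.1 defines the primary endpoint as the difference in mean RNFLT from baseline to month 36, or to the last value if month 36 is missing, in the full analysis set. It adds that "Mean RNFLT is the average of valid measurements of the right and left eye". SAP 1.2 places the averaging at the level of the visit: "The average RNFL thickness following OCT assessment will be calculated for the left and right eye per visit and per patient".

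The definition of the last value, which follows the objectives table, says that "missing or invalid data are replaced by the last available value. Baseline values are not carried forward". It does not say whether this is done for each eye or for the patient's mean. SAP 2.5.3 adds a second analysis: "An analysis without replacing the missing data is performed as sensitivity analysis".

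Two other rules bear on the point. SAP 2.7.3 describes the full analysis set by the condition that "at least one post-baseline value of the primary parameter is required", which one eye can satisfy. In SAP 5.4, Table 1, deviation O1 reads "Baseline OCT measurements not performed". It removes a patient from the per-protocol set only, and does not say whether one missing eye is enough.

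Protocol 7.3 schedules OCT for both eyes at every visit from baseline on, so a one-eye mean arises only when a scan is missing or invalid.

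**The concern.** Averaging first and subtracting second is harmless only if the same eyes enter both averages. If they differ, the subtraction mixes change over time with the fixed difference between a patient's two eyes.

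That fixed difference need not be small. Protocol section 1 states that "visible RNFL thinning by OCT may be seen when inflammation causes degeneration of axons within the optic nerve", for example after optic neuritis. Exclusion criterion 12 bars only acute optic neuritis in the six months before screening, so eyes with an older history are admitted, and a secondary objective compares eyes with and without that history. The quantity to be measured, by contrast, is slight: the same section says that the thickness itself and "the amount of change that may occur, however, are both very small (few microns").

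The study tests no hypothesis (SAP 2.5.2), so its main product is the estimate of change. What is at stake is the accuracy of that estimate, and whether two programmers working from this SAP would obtain the same one.

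**Working it through.** No figure in the plan depends on this rule, so there is none to reproduce.

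**One patient.** Let R and L be the two eyes, 0 baseline and 36 month 36, with both eyes valid at baseline and only R at month 36:

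R36 − (R0 + L0)/2 = (R36 − R0) + (R0 − L0)/2.

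The first term is the real change. The second is half the baseline gap and contains no change over time. With zero true change and D = R − L, the rule gives:

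| Eyes at baseline → month 36 | False change |
|---|---|
| both → R only | +D/2 |
| both → L only | −D/2 |
| R only → both | −D/2 |
| L only → both | +D/2 |
| R only → L only | −D |
| L only → R only | +D |
| same eye or eyes at both times | 0 |

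A gap of 3 µm gives 1.5 µm; a gap of 10 to 20 µm gives 5 to 10 µm.

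**Does carry-forward repair it?** On the patient mean, it is never triggered while one eye is valid, since the mean is not missing. Per eye, it repairs an eye lost at month 36 that had an earlier valid post-baseline scan. Three cases remain:

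- an eye invalid at baseline;
- an eye with no valid scan after baseline, because baseline values are not carried forward;
- the sensitivity analysis without replacement.

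**The group.** The documents give no inter-eye gap, SD of change or invalid-scan rate, so these inputs are assumed: 100 patients; true change −1.5 µm; share with unequal eyes s = 0.5; gap D = 10, 15 or 20 µm; share losing one eye p = 0.10; between-patient SD of change 2.0 µm; noise per scan 1.0 µm. A two-eye mean has noise variance 1/2, so a difference of two such means has 1, and the clean SD is √(4 + 1) = 2.24 µm. With q the probability that the thinner eye is the one lost:

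- size of shift in the mean = p × s × (D/2) × (2q − 1). At q = 1: 0.10 × 0.5 × 5, 7.5 or 10 = 0.25, 0.375 or 0.50 µm. At q = 0.5: 0.
- SD under random loss = √(5 + p × s × (D/2)²) = √6.25, √7.81 or √10 = 2.50, 2.80 or 3.16 µm.

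A simulation of six visits under the same inputs agrees (values for D = 10 / 15 / 20 µm):

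| One eye lost in 10% of patients | Carry-forward | Mean if thinner eye always lost | Random loss: mean; SD |
|---|---|---|---|
| at month 36 | not per eye | −1.25 / −1.13 / −1.00 | −1.50; 2.50 / 2.78 / 3.14 |
| at month 36 | per eye | −1.47 to −1.48 | −1.47 to −1.48; 2.2 |
| at baseline | per eye | −1.75 / −1.87 / −2.00 | −1.50; 2.50 / 2.79 / 3.15 |
| at all post-baseline visits | per eye | as first row | as first row |

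The small shortfall in the second row is ordinary carry-forward. With linear change the month-24 value is −1.0 µm, so 0.10 × ½ × 0.5 = 0.025 µm is lost. At p = 5% the shifts halve, to 0.13 to 0.25 µm.

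Taking the change within each eye and then averaging gives −1.47 to −1.51 µm with SD 2.2 to 2.3 µm in every row.

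**The case against.** The algebra is not in dispute; the reach and size are. The best counter-argument is that the SAP probably intends carry-forward per eye. It applies the idea of validity to measurements of each eye, and SAP 5.3.2 already builds a change to last value for each eye. On that reading most follow-up losses are repaired. An eye never valid at any of up to five later visits should also be much rarer than one failed scan, so 10% is generous there. This stands. The firmest remaining case is an eye invalid at baseline, whose frequency the documents do not give.

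Group bias needs loss that depends on thickness, and no passage links the two. With milder inputs (p = 2%, q = 0.75, D = 10 to 20 µm) the formula gives only 0.02 × 0.5 × 5 or 10 × 0.5 = 0.025 to 0.05 µm. Under random loss with D = 10 µm and n = 100, the standard error rises only from 0.22 to 0.25 µm. This also stands.

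The proposed rule looks near perfect partly because both eyes were assumed to change alike. If thinner eyes change differently and are lost selectively, it is biased too, but by half the difference in change, not half the difference in level. A 1 µm difference in change gives 0.10 × 0.5 × 0.5 = 0.025 µm, against 0.25 µm from a 10 µm gap under the written rule.

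The mixed model in SAP 2.5.4 uses within-eye change and is free of the artefact, but it addresses the optic neuritis comparison. Boxplots and the normality check may expose outliers, but do not correct them. Finally, part of SAP section 2 before 2.2 is not visible in the copy reviewed, so a same-eye rule there cannot be fully excluded. Sections 2.5.1 to 2.5.3 and 5.3 contain none.

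**Conclusion.** The concern holds. Followed as written, the rule gives an affected patient a false change of half the inter-eye gap, or the whole gap if the only valid eye switches. This part is exact and needs no assumption.

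The effect on the group mean is conditional. It is zero in expectation if eye loss is random, with the SD rising from 2.24 to about 2.5 to 3.1 µm in the assumed setting. It is 0.25 to 0.50 µm, or 17% to 33% of an assumed −1.5 µm, if 10% of patients lose an eye and it is always the thinner one. The sign depends on timing: loss at baseline exaggerates thinning, and loss at follow-up hides it. Carry-forward per eye, if that is what is meant, confines the problem in the main analysis to eyes invalid at baseline or never valid afterwards.

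In a descriptive study this is no threat to a formal test, but the definition of the primary estimate should be corrected.

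**What to change.** Before database lock:

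- In SAP 1.2 and 2.5.1, define the change for each eye as its month-36 value (or its last valid post-baseline value) minus the same eye's baseline, and average over the eyes that have both.
- In 2.5.3, state that carry-forward works per eye, and that the analysis without replacement uses only eyes valid at both visits.
- In 5.4, say whether one missing baseline eye counts as deviation O1.
- Apply the same rule to the ratios and to the quadrant, TMV and GCIP averages.
- Report how many patients contribute one eye and how many two.

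The cost is a few sentences and a reordered derivation. SAP 5.3.2 already needs the per-eye changes for RNFLT. A patient with no eye valid at both times contributes no change. In the no-replacement analysis this is about 0.10 × 0.10 × 0.5 = 0.5% of patients, if 10% lose one random eye independently at each of the two visits.

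Separately, the LSMEANS statement in 5.3.2 names `krank`, which is in neither the CLASS nor the MODEL statement. It should name `opt_neur`.

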2.5.2 Statistical hypothesis, model, and method of analysis

No hypothesis is to be tested.

Descriptive pairwise comparisons are performed using a paired t-test in case of normality, In case of non-normality a Wilcoxon signed-rank test is applied instead. No adjustment for multiple comparisons are made. For each parameter the normality distribution is graphically proved for the change from BL to M36. Differences as well as pre-post ratios are displayed. When non-normality is detected for the change to M36 the changes to M12 respectively M36 are analysed also non-parametrically.

The primary efficacy variable is presented graphically by standard boxplots for each time point. Sample statistics are presented for each time point and changes (differences as well as ratios) to each time point.

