10.5 Analysis of secondary [REDACTED] objectives

10.5.1 Secondary [REDACTED] outcomes

Secondary endpoints like changes in quadrant RNFLT, changes in total macular volume (TMV), and changes in ganglion cell layer thickness (GCLT) from baseline to months 12, 24, and 36 will be evaluated with a paired t-test or Wilcoxon signed-rank test, as appropriate.

Changes in OCT parameters between eyes with and without history of optic neuritis will be evaluated with a paired t-test or Wilcoxon signed-rank test, as appropriate.

[REDACTED]

Additionally, means, standard deviations, median, minimum and maximum will be presented for each visit, as will be the change from baseline. These descriptive statistics will also be presented for the primary endpoint.

For all other [REDACTED] endpoints summary statistics will be presented. Summary statistics will include n (number of observations), mean, standard deviation, median, minimum and maximum values at each visit, as well as the change.

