2.8.1 Adverse events (AEs)

Adverse events which started before BL/M0 were listed only. Analyses were performed on AEs which started at/after BL/M0.

The incidence of adverse events is displayed with n, percentage and 95% confidence interval for the SAF. Here, different types of AEs are presented:

- (1) Any AE
- (2) AE with suspected relationship to fingolimod
- (3) AE leading to study drug dosage adjustment/temporary interruption
- (4) AE leading to permanent study drug discontinuation
- (5) Serious adverse event
- (6) Non-Serious AE
- (7) Death

For AEs of type (1) to (6) a two-level frequency table for MedDRA system organ classes (SOC) and Preferred Terms (PT) within SOC are presented. Here, a patient with multiple occurrences is counted only once on the respective class.

The maximum severity of (several) AEs occurring in a patient ist displayed for PTs within SOC, SOC and overall.

For AEs of type (7), (5), and (3) separate listings are generated.

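### The test for each OCT change is chosen from a plot of the outcome, and no confidence interval is named for any OCT change in a single-arm study that aims to estimate it

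*SAP*

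**What the plan says.** SAP 2.5.2 opens with "No hypothesis is to be tested". For the comparisons with baseline it continues: "Descriptive pairwise comparisons are performed using a paired t-test in case of normality", and then "In case of non-normality a Wilcoxon signed-rank test is applied instead". The choice rests on a visual check: "For each parameter the normality distribution is graphically proved for the change from BL to M36". No numerical or descriptive criterion for that check is given. If the month-36 change looks non-normal, "the changes to M12 respectively M36 are analysed also non-parametrically". SAP 2.7.2 applies a similar analysis to the secondary OCT endpoints and labels the p-values descriptive. Protocol 10.4.2 plans the same pair of tests for changes to months 12, 24 and 36.

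The tests are not the only output. SAP 2.5.2 adds boxplots and this: "Sample statistics are presented for each time point and changes (differences as well as ratios) to each time point". Protocol 10.5.1 says that "means, standard deviations, median, minimum and maximum will be presented for each visit, as will be the change from baseline" and extends this to the primary endpoint. The number of observations is part of the protocol's summary statistics (10.2 and 10.5.1).

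The visible text names no confidence interval for any OCT change. SAP 2.8.1 does plan one for safety: "The incidence of adverse events is displayed with n, percentage and 95% confidence interval".

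**The concern.** With one arm and no comparator, the useful result is how much the RNFL changed and how precisely that is known. A test against zero change does not answer this. It says whether zero is compatible with the data, but not which amounts of thinning are.

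The method rule adds a second difficulty. The paired t-test addresses the mean change. The signed-rank test addresses symmetry about zero, and its natural estimate is a rank-based location (the Hodges-Lehmann estimate). Because the choice follows a plot of each parameter's own outcome data, average RNFLT, the quadrants, TMV and the ganglion cell measure may carry p-values about different quantities. Two analysts could also read the same plot differently.

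Finally, the fallback sentence omits month 24. A programmer who follows it word for word would leave that visit on the t-test while months 12 and 36 switch.

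**Working it through.** **Plan's own figure.** The sample size of about 100 (Protocol 10.7, SAP 3) comes with no SD, effect size, power or precision target. There is nothing to reproduce, and nothing in it is called wrong.

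**Where intervals are named.** Places in the visible text that describe OCT analyses:

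| Place | Planned output | Interval named |
|---|---|---|
| Protocol 10.4.2 | graph, absolute and percent change, t-test or Wilcoxon | no |
| Protocol 10.5.1 | mean, SD, median, minimum, maximum; tests | no |
| SAP 1.2, 2.5.1 | differences and ratios | no |
| SAP 2.5.2, 2.7.2 | sample statistics, boxplots, tests, correlations | no |
| SAP 2.5.4, 5.3.2 | least-squares means, difference with p-value; code has no confidence-limit option | no |
| SAP 2.8.1 (adverse events, for contrast) | n, percentage | yes, 95% |

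**The month in the fallback.** The month-36 change triggers the switch, so naming month 36 again as its consequence adds nothing. SAP 1.2 pairs month 12 with month 24 for the secondary RNFLT endpoint, and Protocol 10.4.2 applies one rule to months 12, 24 and 36. Month 24 is evidently meant.

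**Size of the unprinted interval (illustration).** Half-width = t(0.975, n−1) × SD/√n. The SD of 3–6 µm and n = 70 are assumptions.
- n = 100: 0.198 × SD, so 0.60 µm at SD 3 and 1.19 µm at SD 6.
- n = 70: 0.238 × SD, so 0.72 µm at SD 3 and 1.43 µm at SD 6.

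Protocol section 1 puts both RNFL thickness and its likely change at a few microns, so such widths would matter to a reader.

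**What a p-value alone conveys.** At n = 100, a two-sided p of 0.04 corresponds to a mean change of 0.208 SD, with 95% interval 0.010 to 0.407 SD. At an assumed SD of 6 µm that is 0.06 to 2.44 µm (0.010 × 6 and 0.407 × 6).

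**That the two tests have different targets.** Simulation with n = 100, 2,000 runs and true mean change zero. Shapiro-Wilk at 0.05 is an assumed stand-in for the plot, and the skewness values are also assumed.

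| Skewness | t-test rejects | Wilcoxon rejects | Chosen test rejects |
|---|---|---|---|
| 0 | 5.7% | 5.0% | 5.8% |
| 0.5 | 5.0% | 7.2% | 6.3% |
| 1.0 | 4.8% | 12.8% | 12.8% |
| 1.4 | 5.3% | 22.1% | 22.1% |

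With skewed data, Wilcoxon rejects although the mean change is zero, because it does not test the mean. The t-test stays near 5% throughout, which supports keeping the mean as the fixed target at this sample size.

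**The case against.** The strongest reply is that the amount of thinning is reported. Mean and SD of change are planned whichever test is used, and with n a reader can compute the t-based interval. This stands, so it would be wrong to infer that the p-value is the sole result or that the uncertainty is lost. Only a Hodges-Lehmann interval could not be recovered from those summaries.

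A reader might also infer that testing contradicts the statement that no hypothesis is tested, or that error rates are inflated. The documents do not support this. The SAP calls the comparisons and p-values descriptive, and both documents call the study explorative. The simulated rejection rates do not measure this plan's performance either: they score Wilcoxon against a null it does not test, under assumed skewness and a formal test in place of a visual check.

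A reader might further infer that the endpoint itself depends on the data, or that visits are meant to be analysed differently. Neither holds. SAP 2.5.1 fixes the endpoint as the difference from baseline to month 36, and only the accompanying test switches. The rule is plainly meant to carry one method across visits, and the omission of month 24 is a slip.

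Lastly, most of the SAP text before section 2.2 is not available, and the visible SAP does not define its sample statistics. A definition that includes an interval could lie there.

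**Conclusion.** The point holds as a weakness of reporting and of method choice. The test is selected for each OCT parameter from its own outcome plot without a criterion, so the inferential target can differ between parameters. No interval for OCT change is named in the visible text of a study whose purpose is estimation. The wording that omits month 24 needs correcting because a SAP may be programmed as written.

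The micron half-widths are illustrations that scale directly with the assumed SD, and the smaller n is also assumed. The finding itself does not depend on them. The absence of an interval is established for the visible text only.

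**What to change.** In SAP 2.5.2, and through it 2.7.2:
1. Make the mean change from baseline with a t-based 95% confidence interval the main result at months 12, 24 and 36 for every OCT parameter, whatever the plot shows.
2. Give the Wilcoxon signed-rank test with a Hodges-Lehmann estimate and interval as a sensitivity analysis at all three visits.
3. In the fallback sentence, change M36 to M24 if that sentence is kept.

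The cost is a few lines of SAP wording and an output option in the programs. No new data and no design change are needed.
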